5. SAMPLE SIZE CALCULATION

The sample size for this clinical investigation was based on the primary efficacy endpoint. Based on the VMDN-002 and VMDN-003b findings, the standard deviation of the pain score change from baseline is assumed to be 2.18. Table 3 provides the summary statistics for the corresponding efficacy endpoints based on change in the Average Daily Pain Score for the low- dose and placebo groups from the ITT population and efficacy population in the VMDN-002 trial as well as the mean and standard deviation of change from baseline in the ITT population in the VMDN-003b trial.

Table 3: Mean and Standard Deviation of Pain Score Changes from Baseline in VMDN-002 and VMDN-003b Trials

Trial (Population)	Placebo	Engensis	Mean Difference	Placebo STD	VM202 STD	Pooled STD
VMDN-002 (ITT population)	-1.63	-2.58	0.95	1.76	2.19	2.08
VMDN-002 (Efficacy population)	-1.59	-2.78	1.19	1.89	2.24	2.18
VMDN-003b (ITT population)	-1.49	-2.52	1.03	1.77	2.23	2.13

Abbreviations: ITT, intent-to-treat; STD, standard deviation.

The estimates presented in Table 4 consider a range of scenarios. Following a careful review, the maximum sample size is 250 participants. The target sample size is 152 participants and is based on the following assumptions:

- Mean difference between active and control of 1 point
- Common standard deviation of 2.18 units
- Randomization ratio: 1:1
- 2-sided test with a type 1 error rate of 5%

Table 4: Sample Size Scenarios

Scenario	Primary Endpoint Mean Difference (Engensis minus Placebo)	Nominal Power	Actual Power	Total Sample Size
1	-1	80%	0.802	152
2	-1	85%	0.853	174
3	-1	90%	0.900	202
4	-1	95%	0.951	250
5	-1.2	80%	0.802	106
6	-1.2	85%	0.854	122
7	-1.2	90%	0.903	142
8	-1.2	95%	0.951	174

VMDN-003-2 Version 7.0

When 50% of the minimum target sample size (76 subjects) has been enrolled and completed or withdrawn prematurely, a re-estimation of the sample size based on the conditional power will be conducted based on the method described by Mehta and Pocock.²

The maximum sample size of 250 will provide 95% power for the treatment difference of 1.0 point when other assumptions are held the same. Simultaneously, the maximum sample size of 250 is considered an appropriate sample size to claim statistical significance for the clinically meaningful difference with an effect size of \geq 0.3.

Independently of the interim assessment, an effect size of 0.3670 (Mean Difference/SD=0.8/2.18) translates into an overall power of 82.4%. While this is on the cusp of what is considered a small to moderate effect, this can also be described as an observed difference (active minus control) of -0.8 units with 250 subjects, based on the original planning estimates.

An effect size of 0.3440 (0.75/2.18) would still be on the cusp of what is considered a small to moderate effect; this translates into an observed difference (active minus control) of -0.75 units with 250 subjects, based on the original planning estimates.

An effect size of 0.3211 (0.7/2.18) would still be considered a small yet meaningful clinical effect; this translates into an observed difference (active minus control) of -0.7 units with 250 subjects, based on the original planning estimates.

Clinically, a small effect size of 0.3 would still offer benefit in the form of pain relief to the subjects; this effect size needs to be considered relative to the risk of taking the drug. Therefore, maximum sample size of 250 subjects would not allow for a statistical result that is significant (p<0.05) with an effect size of <0.3; this would not be considered clinically meaningful.

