### **5.3. Number of Participants**

The target sample size is a minimum of 152 Participants with a maximum sample size of 250 Participants. Participants will be randomized in a 1:1 ratio. Based upon the results of the adaptive design interim analysis, which will include at least 76 completed or discontinued Participants, the number of Participants randomized may be increased to a maximum of 250 Participants. The adaptive design provides for re-estimation of the sample size after 50% of Participants have completed their 6-month assessments or have discontinued. The total enrolled number of Participants may be increased to a maximum of 250 Participants if the results are promising (conditional power > 39.6%). The adaptive design process is described in the Statistical Analysis Plan (SAP).

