### 9.1. Sample Size Determination

The sample size for the primary efficacy endpoint is calculated based on the hypothesis for the primary efficacy endpoints.

The primary efficacy endpoint is the change in the mean ADPS recorded at the Day 0 and Day 180 Visits obtained from 5 to 7 daily entries in the BPI-DPN eDiary prior to those Visits.

The statistical hypothesis for the primary efficacy endpoint (Hypothesis I) is:

$$H_0: \mu_t = \mu_p \text{ versus } H_a: \mu_t \neq \mu_p, (I)$$

where  $\mu_t$  and  $\mu_p$  are the mean pain change from Baseline to 6-month follow-up for the Engensis and Placebo groups, respectively. A negative mean value means a reduction in the pain score, and a positive mean value means an increase in the pain score. The statistical power is 80%.

Details on the assumptions for sample size determination are described in the Statistical Analysis Plan.

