7.2. Visit Windows

Data at each scheduled follow-up visit will be analyzed according to the nominal visit identified on the data record.

In case of multiple different visits with the same nominal visit designation, the visit with the visit date closest to the target days of each protocol-specified visit schedule will be used for the efficacy analyses. For visits with the same distance to the target days, the later nominal visit record will be used. Data from all visits will be provided in the data listings.

If a subject fails to complete a study visit but provides necessary eDiary data during the time period expected for that visit (i.e. based on study day relative to the date of the first dose in VMDN-003-2), those eDiary data will be used to derive applicable endpoints. Day 90 endpoint would be derived by the eDiaries recorded 7 days up to 90 days from the date of first dose. Also, Day 104 endpoint would be derived by the eDiaries recorded 7 days up to 104 days from the date of first dose. Similarly, Day 180 endpoint would be derived by the eDiaries recorded 7 days up to 180 days from the date of first dose. Otherwise, if subject completes study visit, then date of visit will be used to derive applicable endpoints.

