7.6.1. Missing Pain Scores for the Average Scores from BPI-DPN

The means of the Average Daily Pain Scores (Question 5 from the BPI-DPN) for a visit will be considered as missing if fewer than 5 of 7 days of BPI-DPN eDiary entries are provided. Any missing mean pain score of ADPS will be imputed using the methods described below.

- Multiple Imputation (MI) method:
 - Step 1: Intermittent missing values will first be imputed by treatment group using the Markov Chain Monte Carlo (MCMC) method, resulting in data with a monotone pattern.
 - Step 2: Multiple imputation by treatment group using linear mixed model regression with factors of baseline pain score, baseline HbA1c, gender, and age will be applied to the data

obtained from the MCMC step. The imputed score will be rounded to the first decimal point.

The entire procedure will be repeated 10 times, and 10 complete datasets will be used for the analysis.

Mean of the other group (MOTH):⁴

- 1. For a participant with missing average pain score/the worst pain score in the full BPI-DPN instrument from the 7 days prior to the Day 0 to Day 90, and Day 180 visits, identify the participant's following baseline characteristics:
 - Study treatment group
 - o Baseline Average Daily Pain Score (<median or ≥median)
 - HbA1c (<median or ≥median)
 - o Gender (male or female)
 - Age (<65 years and ≥65 years)
- 2. The missing mean pain score from the 7 days prior to the Day 0, Day 90, and Day 180 visits will be imputed by using the mean pain score obtained at the same time point of those participants in the other treatment group who match the participant's baseline characteristics. For example, for the missing pain scores of the Engensis participants, the mean pain scores of the placebo participants within the same covariate groups will be used to impute the missing pain scores.
- 3. The baseline characteristics will be re-examined for appropriateness and may be re-categorized (due to small sample size) before unblinding the study.
- 4. The imputed score will be rounded to the first decimal point. The imputed scores will be included in the continuous Repeated Measures Model (Section 8.4.1) analysis.

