8.7. Interim Assessment

The interim assessment will be conducted by the IDMC; the details of the procedure are described in the IDMC Charter. Given that much of the programming to derive the estimates will come from this SAP, a summary of the process is outlined below.

After 76 subjects either discontinue or complete the study, representing 50% of the original sample size, the interim analysis will be performed. The interim analysis will be used to re-estimate the sample size based on the following decision rule; the trial may be halted for futility based on the interim analysis results.

- If the conditional power is in the unfavorable zone, <39.6%, the study will be halted; no additional participants will be enrolled.
- If the conditional power is in the promising zone, 39.6% to 80%, the sample size will be increased to a final sample size (N₂, ≤250), where N₂ satisfies the condition that the conditional power is 80%.
- If the conditional power is in the favorable zone, >80%, the study will continue with the original sample size of 152.

The interim assessment will follow the method described in the published paper by Mehta and Pocock,² which states that if "the sample size is only increased when the interim conditional power falls within a certain 'promising zone' then the conventional test will indeed protect the type-I error." The minimum of conditional power is not so small as to result in an inflated overall type-I error using a conventional final analysis. Therefore, implementing the interim analysis for the reestimation of sample size should protect inflation of the type I error rate.

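### Does the sample size of 152 fall short because the SAP states no allowance for missing Day 180 pain scores?

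*SAP*

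**What the plan says.** SAP section 5 introduces its list with "The target sample size is 152 participants and is based on the following assumptions" and names four items: mean difference 1 point, common SD 2.18, 1:1 randomisation, two-sided 5% error. For the upper limit it says "The maximum sample size of 250 will provide 95% power for the treatment difference of 1.0 point". For a 0.8-point difference with 250 participants it says the effect "translates into an overall power of 82.4" per cent, in a sentence that opens by setting the interim assessment aside. Protocol 9.1 says "The statistical power is 80" per cent and refers to the SAP for the assumptions.

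On losses, SAP 8.7 times the interim "After 76 subjects either discontinue or complete the study, representing 50% of the original sample size", and Protocol 5.3 describes the same analysis as one "which will include at least 76 completed or discontinued Participants". The intent-to-treat population (SAP 6.1, Protocol 9.2.1) is everyone randomised. A visit mean "will be considered as missing if fewer than 5 of 7 days of BPI-DPN eDiary entries are provided" (SAP 7.6.1). Missing means are then imputed, by multiple imputation or from matched participants in the other arm. Where a visit is missed but the diary was kept, "those eDiary data will be used to derive applicable endpoints" (SAP 7.2). Protocol 8.3.1 reschedules the Day 0 or Day 180 visit if the diary is short. Neither document gives an expected missing rate.

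**The concern.** A sample size section usually says either that the total has been inflated for dropout or that it counts evaluable participants. This one says neither. Withdrawals count towards the 76 that make up half of 152, and the analysis set is everyone randomised, so 152 reads most naturally as a number randomised. That is explicit for the 76 and an inference for the 152. The power attached to it, however, is the power for 152 observed scores.

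On the plan's own difference and SD there is no slack, since one score fewer takes power below 80%. If the SD of 2.18 were exact and lost scores carried no information, any real loss would make the stated 80%, 95% and 82.4% too high. A reader also cannot tell how much loss the sponsor expects or what is meant to absorb it.

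**Working it through.** **Inputs.** Differences of 1 and 0.8, SD 2.18, totals of 152 and 250, and two-sided 5% come from SAP section 5. Arm SDs and pooled SDs come from SAP Table 3. The missing rates are assumptions. The 2% is close to the one retention figure in the documents, 99 of 101 completing a selected 3-month extension (Protocol 2.2.7.2): 2/101 = 2.0%. The 5% and 10% have no source in the documents.

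**Step 1: reproduce the plan.** For a two-sample t-test with equal arms and total N, the noncentrality is δ / (SD × √(4/N)) on N − 2 degrees of freedom.

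| Case | Noncentrality | Power | SAP |
|---|---|---|---|
| δ = 1, N = 152 | 1 / (2.18 × √(4/152)) = 2.828 | 0.8022 | 0.802 |
| δ = 1, N = 250 | 1 / (2.18 × √(4/250)) = 3.626 | 0.9508 | 0.951 |
| δ = 0.8, N = 250 | 0.8 / (2.18 × √(4/250)) = 2.901 | 0.8238 | 82.4% |

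All eight rows of Table 4 reproduce to within 0.001. At N = 151 the power is 0.7996.

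**Step 2: remove a fraction m of scores.** Replace N by N(1 − m), keep SD 2.18, and recover nothing from participants with missing scores.

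| m | 152, δ = 1 | 250, δ = 1 | 250, δ = 0.8 |
|---|---|---|---|
| 2% | 79.4% | 94.7% | 81.6% |
| 5% | 78.2% | 94.1% | 80.4% |
| 10% | 75.9% | 92.9% | 78.2% |

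**Step 3: check the SD.** Each pooled SD in Table 3 implies a weight w on the Engensis arm through pooled² = w × SD_E² + (1 − w) × SD_P². The three rows give w = 0.72, 0.82 and 0.76. In every row the Engensis arm is the more variable, so pooling at those weights overstates the SD for a 1:1 trial. The 1:1 value is √((SD_P² + SD_E²)/2).

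| Table 3 row | 1:1 SD | N for 80%, δ = 1 | Loss that 152 absorbs | Power at 152, 10% missing |
|---|---|---|---|---|
| VMDN-002 ITT | √((1.76² + 2.19²)/2) = 1.99 | 126 | 1 − 126/152 = 17.1% | 83.2% |
| VMDN-002 efficacy | √((1.89² + 2.24²)/2) = 2.07 | 137 | 1 − 137/152 = 9.9% | 80.0% |
| VMDN-003b ITT | √((1.77² + 2.23²)/2) = 2.01 | 130 | 1 − 130/152 = 14.5% | 82.2% |

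Even without reweighting, the two ITT pooled SDs (2.08 and 2.13) need 138 and 145 scores, so 152 absorbs 9.2% and 4.6%.

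**Step 4: how scores go missing.** A short diary before Day 180 leads to rescheduling, and a missed visit does not lose the score if the diary was kept. What remains is mainly withdrawal and persistent diary non-use. Step 2 also sets aside the imputation and the repeated measures model named in SAP 7.6.1, and the possible baseline pain covariate in SAP 4.6. As an illustration, suppose a covariate has correlation 0.3 or 0.4 with the outcome, so that the SD is multiplied by √(1 − r²). Power at 152 with 10% missing then rises from 75.9% to 79.7% or 82.8%.

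**The case for a change.** The strongest reply is that the SAP offers 2.18 as the assumed SD, not as a dropout allowance. Its margin is therefore accidental, and on the middle row of Table 3 a 10% loss uses all of it. Imputation does not restore full information, covariates enter only after a significance test, and the model text in SAP 8.4.1 is not in the public copy. Protocol 4.3 calls earlier discontinuation acceptable without giving a number. All of this stands. It shows that a sentence is absent from SAP section 5, and a sponsor could usefully add one. It does not show that 152 or 250 is too small.

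A second reply is that the stated powers also leave out the interim rule. For the 82.4% the SAP says so itself. For the 80%, the effect depends on how conditional power is computed, which the visible text does not specify. In simulations with a 1-point difference, SD 2.18 and no missing data, overall power with futility enforced is about 72.8% if conditional power uses the observed trend, and about 83.6% if it uses the 1-point design effect. With futility not enforced the figures are about 83.5% and 85.4%. That is a separate question about the adaptive rule and says nothing about missing scores.

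**Conclusion.** The concern does not call for a change. SAP section 5 is silent on missing Day 180 scores, and its powers assume complete data, but every printed figure is correct for what it computes. The fall below 80% needs three things together: an SD of exactly 2.18, a loss rate the documents do not give, and no recovery of information. Under those conditions it is 0.8, 2.1 or 4.3 percentage points at 152 for an assumed 2%, 5% or 10% missing (80.2% less 79.4%, 78.2% and 75.9%, from rounded values). With the sponsor's own arm SDs weighted for 1:1 allocation, 152 holds 80% with roughly 10% to 17% missing.

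This rests on the Table 3 SDs carrying over to the new trial and on a true difference of 1 point. Within those limits the gap is one of reporting. Stating a missing rate would alter neither enrolment nor analysis, nor how the result is read.

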8.7.2. Site Surveillance

Not all of the data supplied to the IDMC will be fully monitored at the time of the interim assessment. Given that the data extract for the IDMC will occur during the course of the study, it may not be feasible to have all of the necessary study subjects' data monitored, and the database will not be locked. The IDMC will be charged with identification of any investigational sites where the interim data are either incomplete or inconsistent and should not be used in the interim calculation of response. Incomplete or inconsistent data may indicate that the study subject selection by the investigational site requires further review. Possible action, as a result of the recommendation from the IDMC, will include suspension of enrollment for an individual site until the study subject case records can be fully monitored. The objective of the intra-site surveillance is to ensure that failure to complete the study is not a result of inappropriate study subject selection, or failure to adhere to the requirements outlined in the protocol.

Independent of the decisions made by the IDMC, the final analysis will be performed using all of the final and monitored data.

The research questions that will be addressed by the IDMC, relative to site surveillance, covers

efficacy:

[figure not shown]
- Based on the pattern of missing or incomplete data, coupled with the attrition rate, does the IDMC recommend continuing enrollment of study subjects at each of the active investigational sites?
- Are there significant differences within each of the treatment arms across the active sites that may affect the poolability of the results across sites?

The IDMC will make one of following non-binding recommendations to the sponsor after conducting the interim assessment:

- Continue enrolling subjects to the pre-specified target sample size
- Continue enrolling subjects to a sample size that exceeds the pre-specified target sample size but less than or equal to the maximum sample size of 250
- Stop enrolling subjects based on futility

An alpha level adjustment will not be necessary for the conditional power procedure if the conditional power for the primary endpoint is $\geq 39.6\%$.

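### SAP section 5 says 250 participants cannot give p<0.05 with an effect size below 0.3; on its own inputs, observed effects from about 0.25 are significant

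*SAP*

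**What the plan says.** SAP section 5 sizes the trial on four assumptions: "Mean difference between active and control of 1 point", "Common standard deviation of 2.18 units", "Randomization ratio: 1:1", and a "2-sided test with a type 1 error rate of 5" percent. The target is 152 participants and the cap is 250.

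The section supports the cap in three ways:

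- By power: "The maximum sample size of 250 will provide 95% power for the treatment difference of 1.0 point".
- By calling 250 suitable for claiming significance when the effect size is 0.3 or more.
- By an exclusion: a "maximum sample size of 250 subjects would not allow for a statistical result that is significant (p<0.05) with an effect size of <0.3". The SAP adds that an effect that small would not be clinically meaningful.

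The paragraphs leading to the third statement define effect size as mean difference over SD. They restate each value as an observed active-minus-control difference with 250 participants.

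SAP section 8.7 allows the final size to rise to 250 when interim conditional power is between 39.6% and 80%. On the final test, section 8.7.2 says: "An alpha level adjustment will not be necessary for the conditional power procedure" when conditional power is at least 39.6%. The final test therefore stays at the two-sided 0.05 level.

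**The concern.** The third statement claims a property of the design: at 250 participants, significance and an effect size below 0.3 cannot occur together. Whether that is so depends only on the critical value of the test at that sample size, and no derivation of 0.3 is shown.

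If the property is absent, one stated reason for choosing 250 falls away. A reader who relied on it would take p<0.05 at 250 as showing an effect the SAP regards as clinically meaningful. In fact the result could lie in the range the SAP itself calls not meaningful.

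**Working it through.** **Inputs (SAP section 5):** SD 2.18, 1:1 allocation, two-sided alpha 0.05, N = 250 (125 per arm). Alpha is unadjusted at the final test (SAP 8.7.2).

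**Step 1: reproduce the SAP's own figures.** Two-sample t-test power uses the noncentral t with N − 2 degrees of freedom and noncentrality (difference/SD) × √(N/4).

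- N = 250, 0.8 points: 0.367 × √62.5 = 2.90, power 82.4%. The SAP says "an effect size of 0.3670 (Mean Difference/SD=0.8/2.18) translates into an overall power of 82.4" percent.
- N = 250, 1.0 point: power 0.951, as in Table 4.
- N = 152, 1.0 point: power 0.802, as in Table 4.

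The method therefore matches the SAP's.

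**Step 2: smallest significant observed effect.** The t statistic is d × √(N/4), so the critical effect is d = t(0.975, N − 2) × √(4/N).

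At N = 250: 1.9696 × √(4/250) = 1.9696 × 0.1265 = 0.249. In points: 0.249 × 2.18 = 0.54.

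| Final N | Critical observed effect size |
|---|---|
| 152 | 0.320 |
| 172 | 0.301 |
| 174 | 0.299 |
| 200 | 0.279 |
| 250 | 0.249 |

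**Step 3: p-values at N = 250**, from t = d × √62.5 on 248 degrees of freedom.

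| Observed effect size | Points (× 2.18) | Two-sided p |
|---|---|---|
| 0.25 | 0.545 | 0.049 |
| 0.27 | 0.589 | 0.034 |
| 0.29 | 0.632 | 0.023 |
| 0.30 | 0.654 | 0.018 |

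A cut-off of 0.3 at N = 250 would need a two-sided alpha of about 0.018.

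**Step 4: can the interim rule lead there?** Assume conditional power is computed at the observed trend, with the interim at 76. Conditional power for N = 152 is then 39.6% at an interim effect of 0.288 and 80% at 0.415. The cap of 250 applies for interim effects from 0.288 to 0.337.

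An interim effect of 0.30 gives conditional power of 43.8% at N = 152 and 68.9% at N = 250. It is in the promising zone and goes to the cap. If the remaining 174 participants show 0.228, the overall effect is (76 × 0.30 + 174 × 0.228)/250 = 0.250, p = 0.049.

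**Step 5: how often?** Simulation with 2,000,000 trials per true effect, counting results in favour of Engensis. It assumes conditional power at the observed trend, the smallest even final N reaching 80% (capped at 250), and futility stops obeyed although SAP 8.7.2 makes the recommendation non-binding.

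| True effect size | Significant with observed effect < 0.3 | Share of significant results |
|---|---|---|
| 0.20 | 2.1% | 11% |
| 0.25 | 2.4% | 9% |
| 0.30 | 2.4% | 6% |
| 0.459 (planning value, 1/2.18) | 0.9% | 1% |

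At a true effect of 0.30, the final N is 174 or more in about 18% of trials and 250 in about 9%.

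**The case against.** **Nothing operational depends on the sentence.** Success is p<0.05 on the primary endpoint, no criterion uses 0.3, and the cap has a correct basis in 95% power for 1.0 point. Any trial report would also show the estimate itself. This stands, and it limits the point to a correction of text.

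**The event is rare, and its frequency rests on assumptions.** The available SAP text does not say which effect is used for conditional power, and the IDMC Charter is not among the documents. The section's effect-size discussion is also framed as independent of the interim. This is fair: the percentages illustrate scale and are not properties of the plan. The falsity of the sentence needs only steps 2 and 3.

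**The primary model is not an unadjusted t-test.** SAP 7.6.1 refers to a repeated measures model with imputation, and SAP 4.6 allows covariates. The text of SAP 8.4 is not in the available copy, so the exact threshold of the planned analysis cannot be computed. This limits precision only. To move the cut-off to 0.3, variance would have to rise by about 45%, since (0.30/0.249)² = 1.45. No dropout rate is given; as an assumed range, 225, 200 or 175 contributing participants give cut-offs of 0.263, 0.279 and 0.298, all still below 0.3.

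**Effect size might mean the true effect.** The section's own restatement as observed differences points the other way, and the true-effect reading fails too. At N = 250 the chance of significance is about 63% for a true effect of 0.29, 50% for 0.25 and 35% for 0.20.

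**The companion statement also uses 0.3.** Calling 250 suitable for effects of 0.3 or more is not false, because an observed 0.3 gives p = 0.018. It should be read again once the exclusion is corrected.

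**Conclusion.** The concern holds. In an unadjusted comparison of all 250 participants at two-sided 0.05, the threshold for significance is an observed effect of about 0.25, not 0.3. Observed differences of about 0.54 to 0.65 points would be significant while lying in the range the SAP calls not clinically meaningful. The stated limit is true at 152 and up to 172, but false from 174 to the cap.

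The consequence is confined to this one rationale for the cap. It is worth correcting because a confirmatory SAP uses a false property of its design to tie statistical significance to clinical relevance.

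**What to change.** Delete the sentence in SAP section 5, or replace it with wording such as: At N = 250 (unadjusted comparison, all 250 analysed) the smallest significant observed effect size is about 0.25 (0.54 points at SD 2.18), so statistical significance does not by itself show an effect size of at least 0.3.

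The cap can rest on the 95% power statement, which is correct. The cost is one sentence of SAP text, with no change to the test, alpha, interim rule or sample size.
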